6 STUDY DESIGN

This study will utilize a cluster randomized stepped wedge design. Clusters are defined at the level of care teams and qualifying surgical procedures, and have been randomized to one of five different tranches to implement the intervention at staggered intervals (one new cluster each wave, see diagram below).

The primary outcome of the study is a composite of patient reported pain and function at three months post-surgery. This will enable us to determine the effectiveness of a bundled NOHARM Healing after Surgery Guide + clinical decision support for promoting non-pharmacological pain management strategies to patients undergoing qualifying surgeries, which may also ultimately curb overall patient demand for opioid prescriptions in post-acute post-surgical rehab while optimizing functional recovery. Thus, our secondary outcome(s) is opioid use at the 3 month point post-operatively. This will enable us to understand the impact of our EHR-embedded decision support intervention in an era where opioid prescribing is already being constrained.

All patients receiving common, pre-defined procedures within 7 surgical practice areas at 6 Mayo Clinic locations will receive the study intervention if their surgery date coincides with the stepped wedge implementation schedule. Study locations include Mayo Clinic Rochester, Mayo Clinic Florida, and Mayo Clinic Arizona, as well as three Mayo Clinic Health System sites (Mankato, MN; La Crosse, WI; and Eau Claire, WI). Surgical practice areas will include orthopedic surgery, colorectal surgery, gyn surgery, obstetrics, pulmonary/thoracic surgery, liver and kidney transplant, and cardiac surgery. Due to variable combining of post-op unit care areas, practice size, and related considerations we have formed 22 clusters that will be randomized across 5 tranches.

Enrollment in the intervention arm of the trial will extend from March 2021 to approximately August 2023. Participating practices will be enrolled in the study from the point in time the intervention is implemented in their practice and continuing through the end of the study.

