7 SELECTION AND ENROLLMENT OF PARTICIPANTS

7.1 Inclusion Criteria

All patients 18 years of age and older undergoing qualifying surgeries at participating sites will be eligible.

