8.4 Adherence Assessment

Patients will be encouraged, but not required, to interact with the NOHARM Healing after Surgery Guide and to utilize suggested NPPC modalities.

Additionally, patients who are unable or unwilling to interact with the portal-based Healing After Surgery will not provide the NPPC selection data needed to populate and drive the EHR-based algorithms and clinical decision support tools. Therefore, these individuals will be more limitedly exposed to the intervention. They will be encouraged to use the Healing After Surgery Guide during day-of-surgery intake and post-operative care processes, but this may not occur due to many competing demands, or patient preferences.

[figure not shown]
Cognitive limitations, lack of English fluency, or psychiatric illness may result in inability to use the HAS Guide or complete the electronic patient reported outcome measures (ePROMs).

Interaction with the NOHARM HAS Guide, completion of ePROMs and utilization of NPPC modalities will be assessed by time-stamped links associated with the Healing after Surgery Guide while ePROMs and NPPC modality use will be extracted from the medical record.

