12.2 Sample Size and Randomization

Using pain data for 6,261 patients with these procedures at six sites, we estimated the intra-cluster correlation coefficient (ICC) for the pain score to be modest $\rho = 0.037$. To assess minimal detectable effects, we simulated a large number of randomizations and estimated the detectable effect for each. Specifically, for $P = 1, \dots, 5000$ permutations, the 22 clusters were randomly assigned to 5 waves. For each permutation, the closed form solution of Harrison et al (2019) was used to estimate $SE(Q)$ (derived from the formula of Hussey, Hughes (2008)) for true effect Q . We used the values $\sigma^2 = 1$ and $\tau^2 = 0.488$ for the within and between variance components so that detectable effects would be in SDs, and assumed ICC would be 0.037. Over the 5,000 permutations, the detectable effect ranged between 0.048SD and 0.055SD.

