12.4.1 Primary outcome

Physical function and pain interference, as measured with the Patient Reported Outcome Measurement System (PROMIS) computer adaptive tests (CATs) are the co-primary outcomes. The CATs in the Mayo Clinic Epic EHR have been parameterized with stopping rules based on number of items administered rather than a standard error of measurement-defined threshold. IRT-based instruments have generally better discrimination across the entire trait range than legacy PROMs,^{19,20} and CAT administration enhances measurement efficiency and precision.^{21,22} The PROMIS item banks have been validated in the target populations.²³⁻²⁵ The PROMIS physical function and pain interference CATs will be assigned via an automated Epic function precisely 3 months following each patient's surgery. Patients will receive an automated reminder message via their patient portals prompting them to complete the PROMs.

Because post-operative visit requirements and sequences vary across surgical practices, administration of the PROMIS CATs will not be linked to a specific visit, but rather assigned automatically after 3 months have elapsed since surgery. If this data coincides with a clinic visit, then patients will be encouraged to complete the PROMIS CATs via the Epic Welcome interface using a tablet in the waiting room prior to their clinic visit.

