12.5 Data Analyses

Because patients are randomized in clusters, all statistical methods will account for potential correlation of measures within clusters. Such methods include cluster adjusted standard errors for t-tests and χ^2 -tests, and mixed effects models. Patient characteristics will be summarized by intervention status, and tested for difference between intervention groups; any factors which are imbalanced will be accounted for in the main analyses. Factors assessed for balance and potential inclusion in pre-specified analyses are those listed in Section 13.1.1 and all baseline measures listed in 13.1.2.

The primary and secondary outcomes will be compared between intervention groups using mixed effects generalized linear models. Each model will include an indicator for intervention group; a random intercept for cluster; cluster level factors that were used to constrain randomization; calendar time; surgery type; and any patient factors that were imbalanced across groups.

The model details for each outcome are as follows:

1. PROMIS CATs (anxiety (1°), physical function (1°), pain (1°)). These are continuous measures, collected at two time points, pre-operative and 3 months post-operative. To assess the impact of the intervention on these we will estimate three separate models. If Y_{ijt} is the measure at time $t=1,2$ of the i th patient treated by the j th cluster, then we will estimate

$$Y_{ij2} = \beta_0 + \beta_I I_{ij} + \beta_B Y_{ijo} + \beta_T T + \mathbf{B}_X \mathbf{X}_{ij} + \mathbf{B}_Z \mathbf{Z}_j + u_j + e_{ij} \quad (1)$$

where I_{ij} indicates the intervention status, T is calendar time, $u_j \sim N(0, \tau^2)$ is a cluster level random effect, X_{ij} is a vector of patient characteristics, including surgery type, Z_j is a vector of cluster characteristics used for randomization, and e_{ij} is a residual error. By testing $\beta_I = 0$ we can assess whether the intervention is associated with changes in the corresponding measure.

2. NPPC use. This is collected as a binary value for each of 14 modalities, collected at one time point, 3 months post-operative. We will sum these to create a score, and use a model similar to (1) but without a baseline value Y_{ij0} :

$$Y_{ij} = \beta_0 + \beta_I I_{ij} + \beta_T T + \mathbf{B}_X \mathbf{X}_{ij} + \mathbf{B}_Z \mathbf{Z}_j + u_j + e_{ij} \quad (2)$$

Again by testing $\beta_I = 0$ we can assess whether the intervention is associated with changes in the corresponding measure.

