 - PROMIS CATs Questionnaire Followup Message: 3 versions depending on the patient's PROMIS CAT scores; reminds patient of NOHARM resources and if their pain and or physical function is severe, then suggest actions the patient should take
 - **Message sent after opioid prescription refill**

Epic Components (Standard of Care)

- - Healing after Surgery Guide is an Epic questionnaire with additional HTML to help patients understand what to expect when recovering from surgery, learn about pain management techniques and to make a plan to manage pain after surgery. There is a [Desktop version](#) and mobile version

- Pre-op questionnaires: Pre-surgery questionnaires are existing PROMIS CAT questionnaires: Pain Interference, Physical Function, Anxiety questionnaires
- 1, 2 and 3 month post-op questionnaires: (Identify intervention patients that need help/struggling; collect data)
- Physical function, Pain Interference, and NPPC usage -and at 3 months a Opioid Usage questionnaire (content complete) along with the PROMIS Anxiety are also given
- [After Visit summary \(AVS\) \(search the folder for AVS to find all files\)](#)
 - Patient facing: Provides patients with information specific to their selected modalities.
 - [Discharge to facility AVS](#): A significant number of NOHARM participants will be dismissed to post-acute care (PAC) facilities, e.g., skilled nursing facilities. For those patients, the AVS content will be directed to clinicians at PAC facilities

Mayo Clinic Care team Support

- [contact]): NOHARM staff will provide Epic and workflow support
- [Department of Nursing Healing after Surgery \(NOHARM\) Intranet page provides a NOHARM overview as well as available NOHARM resources](#)
- [Provider NOHARM Overview and Talking Points \(elevator speech\) reminds the care team of NOHARM](#)
- MyLearning classes: provide a NOHARM overview, set expectations and teach the NOHARM workflow for each role
 - NOHARM: Introduction and Overview (COURSE 502E00NOHM0001)
 - NOHARM: Provider Training(COURSE 502E00NOHM0004)
 - NOHARM Inpatient Nursing Training (COURSE 502E00NOHM005)
 - NOHARM: Outpatient Nursing Training(COURSE 502E00NOHM0002)
 - NOHARM: Physical Therapy Training (COURSE 502E00NOHM0003)
 - NOHARM: Pre/post-op and PACU Nursing Training (COURSE 502E00NOHM0006)

Epic Components (Standard of Care, support for clinical team)

- [NOHARM Just in Time Training: role based training that is linked in the Epic NOHARM banner](#)
 - [Inpatient nursing](#)

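### Model (1) needs a pre-operative PROMIS score and the plan has no rule for a missing one, so observed 3-month outcomes would drop out of both co-primary analyses unless a rule is added

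*Combined protocol and SAP*

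**What the plan says.** Section 12.4.1 states that the physical function and pain interference "computer adaptive tests (CATs) are the co-primary outcomes". Section 12.5, item 1, fits a separate mixed model (1) to each of these and to anxiety. The 3-month score is the response and the pre-operative score is a fixed covariate. The section describes the scores this way: "These are continuous measures, collected at two time points, pre-operative and 3 months post-operative". The baseline term is deliberate, because for NPPC use the plan will "use a model similar to (1) but without a baseline value".

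Five other places bear on whether the baseline will exist:

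- Section 7.1: "All patients 18 years of age and older undergoing qualifying surgeries at participating sites will be eligible". Section 7.2 lists no exclusions, so a baseline score is not a condition of enrolment.
- Appendix B: "Pre-surgery questionnaires are existing PROMIS CAT questionnaires".
- Section 12.4: scores are taken through the portal, or on a clinic tablet where one is to hand.
- Section 8.2: paper forms for pain and physical function may be sent to some patients at 1, 2 and 3 months after surgery. No paper form is described before surgery.
- Section 8.4: cognitive impairment, limited English or mental illness "may result in inability to use the HAS Guide or complete the electronic patient reported outcome measures (ePROMs".

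The document contains no imputation method, no rule for a missing baseline, no completion target and no sensitivity analysis for missing scores.

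**The concern.** A mixed model copes with a missing response but not with a missing right-hand covariate. Standard software fitting model (1) as written deletes any patient without a pre-operative score, even when the primary outcome is in hand. The 1- and 2-month scores do not bring that patient back, because they are not in the model.

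This differs from ordinary loss to follow-up. The outcome has been collected and would be discarded. The analysed population would narrow from all adults having a qualifying operation to those who also completed a questionnaire beforehand. If the make-up of that group changed when a cluster was activated, the comparison between conditions would be affected as well.

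The loss can compound. Section 12.5 allows imbalanced factors, including the baseline measures in section 13.1.2, to enter the models. That list includes further questionnaires, such as the pain catastrophizing scale and PHQ-4. The subgroup analyses in section 12.6.1 repeat the primary analyses and inherit the same deletion.

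**Working it through.** **The plan's own figure.** The only precision figure is a detectable effect of 0.048 to 0.055 SD (section 12.2). Alpha, power and patients per period are not stated. I used the Hussey-Hughes variance with 22 clusters, six periods, a residual variance of 1, equal periods, two-sided alpha 0.05 and all 114,000 patients. The SE is 0.0106, so the detectable effect is 0.0106 × (1.96 + 0.84) = 0.030 SD at 80% power, and 0.034 SD at 90%. The stated range corresponds to about 33,000 to 44,000 analysed patients at 80% power, or 44,000 to 59,000 at 90%. With those inputs unstated, the figure can be neither confirmed nor faulted, and one cannot tell whether it allows for missing scores. The between-cluster variance hardly matters (0.0298 SD with 0.488, 0.0297 SD with 0.0384), so patient-level information can be treated as roughly additive.

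**Precision.** Let c be the share of 3-month responders with a baseline and r the baseline-outcome correlation. Both are assumed, because the document gives neither. With outcome variance 1, a patient with a baseline contributes information 1/(1 − r²), and a patient without one contributes 1.

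- Complete-baseline analysis: c/(1 − r²)
- Analysis keeping everyone: c/(1 − r²) + (1 − c)
- SE ratio: √[1 + (1 − c)(1 − r²)/c]

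| r | c = 0.8 | c = 0.6 |
|---|---|---|
| 0.5 | √(1 + 0.25 × 0.75) = 1.09 | √(1 + 0.667 × 0.75) = 1.22 |
| 0.7 | √(1 + 0.25 × 0.51) = 1.06 | √(1 + 0.667 × 0.51) = 1.16 |
| 0 | 1/√0.8 = 1.12 | 1/√0.6 = 1.29 |

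The last row is an upper limit. It applies only if a patient without a baseline carries as much information as one with it. Strong predictors of the missing baseline would move the ratio towards that limit.

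If the method lets the mean baseline differ by condition, such a patient contributes c/[c + (1 − c)r²] instead of 1. The ratios become 1.08 and 1.20 at r = 0.5, and 1.06 and 1.12 at r = 0.7.

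**Break-even.** The complete-baseline model is less precise than an unadjusted analysis of all responders once (1 − r²)/c exceeds 1, that is, when c < 1 − r². The threshold is 75% at r = 0.5 and 51% at r = 0.7.

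**Bias.** The following is an illustration under no true effect, with every parameter assumed. The outcome depends on baseline (coefficient 0.5) and on an unmeasured trait (0.3), and the trait also affects baseline completion.

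| Completion, control → activated | Bias in complete-baseline model |
|---|---|
| 60% → 60% | about 0 |
| 50% → 60% | 0.011 to 0.018 SD |
| 50% → 70% | 0.023 to 0.041 SD |

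The ranges reflect a weaker and a stronger link between the trait and completion. Filling in a constant and adding a missing-baseline indicator left the bias about the same: 0.010 to 0.021 SD and 0.024 to 0.045 SD in the last two rows.

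**The case against.** - **The plan does not prescribe a complete-case analysis.** This stands. Deletion is the default result of silence, which is why the point is worded as what would happen unless a rule is added.
- **Baseline completion may be high.** This stands; no rate is given. A reader might infer low capture by setting the 6,261 patients in section 12.2 against the planned 114,000. The documents do not support that. The text, "Using pain data for 6,261 patients with these procedures at six sites", describes the source of an intra-cluster correlation. It gives no period, number eligible, instrument or timing relative to surgery, so the ratio is not a completion rate.
- **Activation does not prompt the baseline.** A reader might infer that the messages and reminder in an activated cluster are requests for the pre-operative PROMIS scores. Section 8.1 and Appendix B show that they concern the Healing after Surgery Guide, and the tablet is a second route to the score. What remains is plausible spillover, because activation adds pre-operative portal traffic and staff encouragement to use the portal (section 9.2.1).
- **Unscheduled surgery is not described.** The practice areas include "colorectal surgery, gyn surgery, obstetrics, pulmonary/thoracic surgery, liver and kidney transplant, and cardiac surgery", so a reader might assume that urgent cases have no time for a questionnaire. Sections 7.3 and 9.2.1 speak only of scheduled surgery. This is an assumption, and the point does not need it.
- **Some patients will lack both scores.** Those unable to complete electronic measures may also have no 3-month score, and this fix does not help them. The paper route in section 8.2 is where an outcome without a baseline is most clearly foreseeable.
- **Model (1) already adjusts.** It conditions on baseline, surgery type and imbalanced factors, so selection would bias the estimate only through what those leave unexplained. This stands, and the bias figures are therefore illustrations, not estimates.

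**Conclusion.** The gap is real and should be closed. The specified model, with no missing-baseline rule, would discard observed co-primary outcomes, and the document's own collection arrangements make such patients foreseeable. If 20% to 40% of responders lack a baseline, the avoidable inflation of the standard error is about 6% to 22% for correlations between 0.5 and 0.7, and at most 12% to 29%. These sizes rest on assumed completion and correlation.

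That the effect estimate is biased is a stronger conclusion, and the documents do not establish it. It requires baseline completion, or selection into it, to differ by activation. If completion is incomplete but unrelated to activation, the loss is precision and generalisability.

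**What to change.** State in section 12.5 that the primary analysis includes every patient with a 3-month score, and name one of two methods:

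- a joint model with baseline and follow-up scores as responses; or
- multiple imputation of the missing baseline.

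The imputation model must be compatible with model (1). It should include condition, calendar time, cluster as a random effect, procedure, the factors used to constrain randomisation, age, sex, comorbidity, prior-year opioid prescriptions and the post-operative scores. Calendar time and cluster matter because condition is tied to both in a stepped wedge. Do not rely on a missing-indicator term alone. Apply the same rule to any other baseline questionnaire brought into the model for imbalance.

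Report baseline completion by cluster and condition, so that readers can see whether it moved with activation. Keep the complete-baseline analysis as a sensitivity analysis.

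The cost is plan wording and some multilevel imputation or joint-model code; no new data are needed. The downside is a missing-at-random assumption for the covariate. If completion depends on something unmeasured that also affects outcome, neither method is guaranteed to remove the resulting bias, which is a further reason to report completion.

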12.4.2 Secondary outcomes

Secondary outcome measures will include opioid consumption, NPPC use, healthcare utilization and anxiety. Anxiety will be measured in a manner similar to physical function and pain interference with a PROMIS CAT administered via the Epic MyChart portal or the Welcome tablet interface prior to a clinic visit that coincides with the 3-month post-surgical time point.

Opioid consumption will be collected using three methods. First, opioid consumption per hospital day, will be extracted from the medication administration log in the EHR. As in previous work,²⁶⁻²⁸ parenteral, transdermal, and oral opioid consumption will be expressed as oral morphine equivalents (OMEs). Second, oral and transdermal opioids prescribed by a Mayo Clinic provider at the time of hospital discharge and during the interval between hospital dismissal and the 3 month post-surgical assessment point will be extracted from the EHR and converted to OMEs. Last, because outpatient prescriptions do not accurately capture opioid consumption, patients will be queried at the 3 month post-operative time point regarding their opioid use using a subscale from a validated opioid consumption questionnaire.²⁸

NPPC use will be collected using two methods. First, the frequency with which patients use specific NPPCs during their hospital stays will be

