3. Opioid use will be measured using 4 outcomes:

- a. Hospital-based consumption, daily oral morphine equivalents (OMEs). This is a continuous measure for each day of hospitalization; we will assume that this depends in part on the day post surgery, D_{ij} and model

$$Y_{ij} = \beta_0 + \beta_I I_{ij} + \beta_D D_{ij} + \beta_T T + \mathbf{B}_X \mathbf{X}_{ij} + \mathbf{B}_Z \mathbf{Z}_j + u_j + e_{ij} \quad (3)$$

For this model we will consider D_{ij} as first continuous and then as categorical.

- b. Discharge and post-discharge prescriptions, daily oral morphine equivalents (OMEs). For this outcome, we will use a model analogous to (3), where D_{ij} is replaced by number of days post discharge.
- c. Number of post-discharge prescriptions. These are counts for the 3 month period following surgery. The impact of the intervention will be assessed using a model similar to (2) but with a Poisson link function:

$$\ln(E(Y_{ij})) \sim \beta_0 + \beta_I I_{ij} + \beta_T T + \mathbf{B}_X \mathbf{X}_{ij} + \mathbf{B}_Z \mathbf{Z}_j + u_j + e_{ij} \quad (4)$$

$$Y_{ij} \sim \text{Poisson}(\mu)$$

We will assess the distribution first using an empty model, and potentially adopt a zero inflated Poisson, negative binomial, or zero inflated negative binomial according to the corresponding AIC values.

- d. Daily use of opioids; this is binary outcome collected one time, at 3 months post-surgery. To assess the impact of the intervention we will use a model similar to (4) but with a logit link:

$$\text{logit}(Y_{ij}) \sim \beta_0 + \beta_1 I_{ij} + \beta_2 T + \mathbf{B}_X \mathbf{X}_{ij} + \mathbf{B}_Z \mathbf{Z}_j + u_j + e_{ij} \quad (5)$$

For a-d we can again test $\beta_1 = 0$ we can assess whether the intervention is associated with changes in the corresponding measure.

4. Healthcare utilization

- a. Hospitalizations
- b. ER visits
- c. Calls to surgical practice

All three of these are count outcomes, and so we will assess the impact of the intervention using a model similar to (4) above. As with (4), we will compare model specifications using an empty model first to determine the best count family (Poisson, negative binomial, zero inflated or not) using AIC, then apply that in the final model.

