Appendix A: Clinician Participants

Clinician Participants

The clinical practices of care teams involved in the care of surgery patients targeted by the NOHARM intervention—including surgeons, nurses, physical therapists, pain management specialists—will be impacted by the bundled NOHARM intervention. In the course of providing care to surgical patients in active intervention clusters, clinicians will be alerted to non-pharmacological pain management strategies (via CDS tools embedded in the EHR) for which patients have expressed preference. Within their routine workflows (i.e. interface with patients), clinicians will be prompted to engage patients about their preferred post-acute pain management strategies.

Because of this practice impact, clinicians will be considered “participants” in the NOHARM pragmatic trial (in the same way as they have been construed in the pilot application IRB# 20-001864). This determination has been affirmed by the Mayo Clinic IRB executive committee (January 2020 meeting).

Accrual

Based on data from 2018 on the 22 surgery types targeted by the NOHARM trial (minus neuro / spine surgery which is the focus of the NOHARM pilot trial – IRB# 20-001864) we estimate there to be approximately 225 surgeons in the enterprise who are routinely performing surgery. We will inflate this number to 300 to account for physicians performing one of the target surgery types less frequently. To this figure, we will add 0.5 residents / and 0.5 physician assistants per surgeon (+300). Assuming a median hospital stay of 3 days (9 nursing shift changes), we will add 9 nurses X 300 surgeons (+2700). Finally, assuming 0.5 physical therapist per surgeon and 0.2 integrative medicine specialist per surgeon, we will add 210 clinicians. This brings our total estimated clinician accrual to 3510 participants.

Consent and Data Collection

1. Given the ubiquity of the intervention and the volume of clinicians touched by the trial it will not be practicable to obtain individual consent for participation.
2. Clinician “consent” will be granted in the form of “whole practice consent” granted by individual surgical practice leadership within the institution as a pre-requisite for implementation in specific surgical practices.

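### Model (3) for daily in-hospital opioid use has several rows per patient but no patient-level term, so its standard error is too small if a patient's days are correlated

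*Combined protocol and SAP*

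**What the plan says.** Section 12.4.2 defines the first opioid measure as a daily one: "First, opioid consumption per hospital day, will be extracted from the medication administration log in the EHR". Section 12.5, item 3a, repeats this ("This is a continuous measure for each day of hospitalization") and includes day since surgery as a covariate: "For this model we will consider D_{ij} as first continuous and then as categorical". Day changes within a patient, so the analysis file has one row per patient per hospital day.

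The general rule in Section 12.5 is: "Each model will include an indicator for intervention group; a random intercept for cluster". The term u_j is defined under model (1) and "is a cluster level random effect"; the only other random term is the residual e_ij. In model (3), Y, D and e carry the subscripts for patient and cluster but none for day. The same section does use an explicit time index when it introduces the PROMIS outcomes.

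The section's general statement on correlation concerns measures within clusters. It names cluster-adjusted standard errors for t-tests and chi-square tests, not for the mixed models.

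Item 3b, on discharge and post-discharge prescriptions, borrows the structure: "For this outcome, we will use a model analogous to (3), where" the day term becomes days since discharge. The number of rows per patient is not stated.

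**The concern.** A cluster intercept captures what all patients in a cluster share. It does not capture what one patient's days share, such as that person's pain, tolerance and prescribing. Fitted with only u_j and e_ij, a patient's second and third days count as new independent information, given the cluster and covariates.

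For a covariate that varies within the patient, such as day, this could matter little. The intervention indicator does not vary within a patient, apart from any stay that spans activation. Positive correlation among the days therefore goes directly into the true variance of the intervention effect and is missing from the reported one. The interval is then too narrow, the p-value too small, and a chance difference in daily opioid use could be reported as an effect.

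Opioid use during the 3 months after surgery is a secondary objective (Sections 1.2 and 4.2). Sections 12.7.1 and 12.7.2 reuse models (1) to (5) for moderators and mediators, so the omission carries into those analyses.

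**Working it through.** The plan gives no standard error or power for outcome 3a, so there is no figure of its own to reproduce. The check is how far the reported standard error falls short.

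**Inputs**
- Days per patient, m = 3. Appendix A gives the only length-of-stay figure ("Assuming a median hospital stay of 3 days"), and it serves there to count nurses. It is used here for scale only.
- Correlation between days of one patient, rho: what remains after day, surgery type, calendar time, covariates and cluster. The document gives none; 0.1 to 0.7 is assumed.
- Test: two-sided 5%, assumed.
- Cluster ICC for the simulations: 0.037, which Section 12.2 gives for the pain score. None is given for opioid use.

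**Formulas**
- Equal correlation between days: DE = 1 + (m − 1) × rho.
- AR(1), m = 3: DE = 1 + 2 × [(2/3) × rho + (1/3) × rho²].
- True SE / reported SE = √DE.
- Type I error = 2 × [1 − Φ(1.96/√DE)].

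Example, rho = 0.5, equal correlation: DE = 1 + 2 × 0.5 = 2.0; √2.0 = 1.41; 1.96/1.41 = 1.39; type I error 16.6%.

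| rho | DE, equal | SE ratio | Type I | DE, AR(1) | Type I |
|---|---|---|---|---|---|
| 0.1 | 1.2 | 1.10 | 7.4% | 1.14 | 6.6% |
| 0.3 | 1.6 | 1.26 | 12.1% | 1.46 | 10.5% |
| 0.5 | 2.0 | 1.41 | 16.6% | 1.83 | 14.8% |
| 0.7 | 2.4 | 1.55 | 20.6% | 2.26 | 19.2% |

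With 5 days and rho = 0.5, DE = 1 + 4 × 0.5 = 3.0 and type I error is 25.8%. Longer stays make it worse.

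**Simulation.** All runs used no intervention effect, 22 clusters, 5 waves and 6 periods, and equal correlation among a patient's days.
- Simulation A: 1,000 datasets per setting, 10 patients per cluster-period (assumed), period effects, linear day trend, REML. Stay was 3 days or 1 + Poisson(2) days.
- Simulation B: 500 datasets per setting, 8 patients per cluster-period (assumed), generalised least squares with known variance components. Stay was 3 days or varied with mean 3.

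Type I error with the cluster intercept only:

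| rho | A, 3 days | A, varying | B, 3 days | B, varying |
|---|---|---|---|---|
| 0 | not run | not run | 4.4% | 4.8% |
| 0.1 | 7.5% | 9.0% | not run | not run |
| 0.3 | 10.7% | 12.5% | 9.6% | 13.2% |
| 0.5 | 15.9% | 18.0% | 14.6% | 17.8% |
| 0.7 | 19.8% | 23.3% | 22.4% | 24.0% |

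Monte Carlo error in A is about ±1.4 points near 5% and ±2.5 points near 20%. Both simulations agree with the formula, and at rho = 0 there is no distortion.

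Adding a patient random intercept gave 3.6% to 5.9% across the eight settings of A, and 4.3% to 7.0% in B (300 runs each, Monte Carlo SE about 1.3 points). In B, with 3 days and rho = 0.5, the mean reported SE rose from 0.0605 to 0.0826, against an empirical SE of 0.079. A smaller check of 200 runs with linear calendar time, as the plan specifies, gave 8.5% to 19% at rho 0.3 to 0.5, and 5% to 5.5% with the patient intercept.

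**Outcome 3b, conditional on its row unit**
- One row per patient: no inflation.
- Two rows, rho 0.2 to 0.5: DE 1.2 to 1.5, type I error 7% to 11%.
- 90 daily rows, AR(1), lag-1 rho 0.2 to 0.5: DE 1.49 to 2.96, 11% to 25%.
- 90 daily rows all equally correlated, rho 0.2 to 0.5: DE 18.8 to 45.5, 65% to 77%. This is an extreme case.

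**The case against.** **The notation can be read differently.** Since i is the patient, e_ij taken literally is shared by all of a patient's days. But that leaves no day-level error, which is not a coherent model for daily values. What stands is that the indexing is incomplete, and treating each row as having its own residual is the likely fit.

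**The plan promises to account for correlation within clusters, and a patient's days lie within a cluster.** The list of methods there is not exhaustive, and cluster-robust standard errors would indeed cover the problem. They are not specified for model (3), so this weakens the point without removing it.

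**The size rests on assumptions.** This is fair. The document gives no within-patient correlation, no cluster ICC for opioid use and no length of stay meant for analysis. Patient covariates, possibly including earlier opioid prescriptions, will absorb part of the correlation. The omission is certain; its size is not.

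**The simulations simplify the plan.** They omit its covariates, and the patient-intercept fit matches the way the data were generated. They show that the mechanism works as the formula says, not that any one covariance structure is right for real opioid data.

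**The consequence is limited.** Outcome 3a is one of four opioid outcomes, and Section 6 describes the secondary outcome as opioid use at 3 months. Sections 1.2, 4.2 and 12.4.2 are broader and do include in-hospital use.

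**Conclusion.** The concern holds. If model (3) is fitted as specified, the standard error of the intervention effect on daily in-hospital opioid use is too small whenever a patient's days are positively correlated after adjustment. With 3-day stays and correlations of 0.1 to 0.7, the formula puts the true error rate of a nominal 5% test at about 7% to 21%; simulated varying stays reached about 24%. These figures depend on the assumed correlation and on a planning figure for length of stay. A larger trial does not help, because the ratio of true to reported standard error stays essentially the same.

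The finding is confined to the standard error of outcome 3a. For 3b it applies only if a patient contributes more than one row. Outcomes 3c and 3d and the co-primary PROMIS models are not affected. It should be fixed before analysis, but it does not threaten the primary result.

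**What to change.** - Index Y, D and e in model (3) by day, and add a patient random intercept nested in cluster, optionally with AR(1) residuals within patient. Keep the planned day term. Alternatively, specify cluster-robust standard errors with a small-sample correction for 22 clusters.
- State whether a row in 3b is a calendar day, a prescription or a patient. Apply the same structure if a patient can have more than one row.
- Carry the revised model into the moderator and mediator analyses that reuse it.
- Use a one-record-per-patient summary as a sensitivity analysis at most, because it changes the estimand and depends on length of stay.

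The cost is a revised equation, a sentence on the 3b row unit and a slightly more complex fit, with no new data. Intervals will be wider where days are correlated. A patient intercept also gives long-stay patients less weight than counting every day equally, so the plan should acknowledge that the estimate may shift if the effect varies with length of stay.
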